When the safety of blinatumomab in combination with nivolumab has been established as above, the trial will proceed to either DL B1 or DL B-1, and a standard 3+3 dose escalation design for blinatumomab and nivolumab with ipilimumab will be used to ascertain the safety of this combination. Two dose levels (DL B-1, DL B1) may be used to evaluate this combination. Depending on the results from the combination of blinatumomab and nivolumab as outlined above, patients will first be enrolled at either DL B1 or DL B-1. If ≤ 1 of 3 patients experiences a DLT at DL B1, an additional 3 patients will be enrolled at DL B1. If ≤ 1 of 6 patients experience a DLT, then this will be defined as the MTD. If ≥ 2 or more of 3 or 6 patients experience a DLT at DL B1, then dose de-escalation may be implemented BUT ONLY after thorough evaluation of toxicities, discussion with CTEP, investigators and CTEP agreement and the next three patients may be enrolled at DL B-1. If the triplet combination starts at DL B-1 based on the results from the combination of blinatumomab and nivolumab alone, then three patients will be enrolled at DL B-1. If ≤ 1 of 3 patients experiences a DLT at DL B-1, an additional 3 patients will be enrolled at DL B-1. If no more than 1 of 6 patients experience a DLT at DL B-1, then this dose level will be defined as MTD. If 2 or more of 3 or 6 patients experience a DLT at DL B-1, then dose escalation will be halted and the combination of blinatumomab, nivolumab and ipilimumab will not be further pursued in this patient population unless additional data become available supporting different doses or schedules of nivolumab and ipilimumab administration. This will require review of all toxicity, discussion with CTEP and official study amendment. The MTD of blinatumomab in combination with nivolumab and ipilimumab is defined as the highest dose at which no more than 1 out of 6 patients experience a DLT. When the MTD of blinatumomab in combination with nivolumab and ipilimumab is determined, an additional 6 patients will be enrolled in an expansion cohort to further characterize safety, tolerability and any preliminary signs of biological or clinical activity. An expansion cohort of an additional 6 patients at the MTD of blinatumomab and nivolumab without ipilimumab will be also pursued to further characterize safety, tolerability and any preliminary signs of biological or clinical activity for this combination. The expansion cohort at the MTD of blinatumomab and nivolumab will be open for enrollment while dose-escalation continues for blinatumomab, nivolumab and ipilimumab. Enrollment priority: Patients will be enrolled in dose-escalation cohort for blinatumomab, nivolumab and ipilimumab first. However, if no slots are available, patients will be allowed to enroll in dose expansion cohort for blinatumomab and nivolumab. Once the MTD for blinatumomab, nivolumab and ipilimumab is defined, the enrollment in dose expansion cohorts

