
for blinatumomab/nivolumab and blinatumomab/nivolumab plus ipilimumab will be 1:1. This amendment was discussed with CTEP on 03/12/2019. Based on safety and efficacy data, the dose level A1 was defined as MTD for blinatumomab and nivolumab combination (1 of 6 patients with DLT; 5 of 6 patients with complete remission).

Dose Escalation Schedule[#]			
Dose Level	Dose		
	Blinatumomab^{&}	Nivolumab	Ipilimumab
All Dose Levels	Nivolumab and ipilimumab (where indicated) will be initiated on Day 11 of Cycle 1		
Level A-1*	9 µg/day IV continuous infusion on Days 1-7 28 µg/day IV continuous infusion on Days 8-28	80 mg IV every 2 weeks	None
Level A1*	9 µg/day IV continuous infusion on Days 1-7 28 µg/day IV continuous infusion on Days 8-28	240 mg IV every 2 weeks	None
Level B-1	9 µg/day IV continuous infusion on Days 1-7 28 µg/day IV continuous infusion on Days 8-28	80 mg IV every 2 weeks	1 mg/kg IV every 6 weeks
Level B1	9 µg/day IV continuous infusion on Days 1-7 28 µg/day IV continuous infusion on Days 8-28	240 mg IV every 2 weeks	1 mg/kg IV every 6 weeks
Safety run-in of blinatumomab and nivolumab: Up to 6 subjects will be treated at dose level A1 and dose level A-1 (if necessary) prior to addition/dose escalation with ipilimumab. [#] Dose expansion of blinatumomab, nivolumab, and ipilimumab: An expansion cohort of 6 subjects will be treated at the MTD. [#] Dose expansion of blinatumomab and nivolumab: An expansion cohort of 6 subjects will be also treated at the MTD for blinatumomab and nivolumab only. ^{&} In Cycle 2 and subsequent cycles blinatumomab will be administered at 28 µg/day IV continuous infusion Days 1-28. Blinatumomab cycles are administered every 42 days.			

Regimen Description					
Agent	Premedications ; Precautions	Dose **	Route	Schedule **	Cycle Length
Blinatumomab	20 mg IV dexamethasone 1 hour prior to initiation in each cycle and at step dose escalation in cycle 1	9 µg/day on Days 1-7 28 µg/day on Days 8-28	Continuous IV infusion	Days 1-28 of each cycle up to 5 cycles	42 days (6 weeks)
Nivolumab	None	80 or 240 mg IV	IV, 30-minute infusion	Day 11, and then every 2 weeks for 1 year ^{&}	
Ipilimumab	None	1 mg/kg	IV, 90-minute infusion	Day 11, and then every 6 weeks for 1 year ^{&}	

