5.2.2 Dose Expansion

An additional 6 patients will be treated at the MTD for both combinations: blinatumomab and nivolumab alone; and blinatumomab/nivolumab plus ipilimumab to gain additional safety information and to explore preliminary biological and clinical activity of these combination therapies. When the MTD of blinatumomab in combination with nivolumab and ipilimumab is determined (either DLB1: Nivolumab 240 mg plus Ipilimumab 1 mg/kg or DLB-1: Nivolumab 80 mg and Ipilimumab 1 mg/kg), an additional 6 patients will be enrolled in an expansion cohort to further characterize safety, tolerability and any preliminary signs of biological or clinical activity of nivolumab and ipilimumab in combination with blinatumomab. However, if the combination of blinatumomab, nivolumab and ipilimumab is found to be intolerable, then the expansion cohort of an additional 6 patients will be only pursued at the MTD of blinatumomab and nivolumab alone (either DLA1: Nivolumab 240 mg or DLA-1: Nivolumab 80 mg) to further characterize safety, tolerability and any preliminary signs of biological or clinical activity for blinatumomab and nivolumab combination.

Based on the review of safety and efficacy data, in discussion with CTEP on 03/13/2019, a separate expansion cohort of an additional 6 patients at the MTD of blinatumomab and nivolumab alone was added to the study in addition to the expansion cohort of nivolumab, ipilimumab and blinatumomab (triple combination) to further characterize safety, tolerability and

any preliminary signs of biological or clinical activity for this combination.

Continuous evaluation of adverse events will be performed throughout enrollment in the expansion cohort. If, at any time, the aggregate rate of treatment-related toxicities meeting DLT criteria exceeds 30% across all subjects treated in the expansion cohort, the safety data will be discussed and further enrollment may be suspended.

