13.3.2 Secondary Objectives

- 13.3.2.1 The frequency distribution of responses, including CR, CRi or progressive disease (PD) by treatment arm and dose level for all patients on study will be determined and reported with exact 95% confidence intervals.

- 13.3.2.2 For patients who have a clinical response, the frequency of MRD+ vs. MRD-responses will be reported by treatment arm and dose level for all patients on study.
- 13.3.2.3 For patients who have a clinical response, duration of response (DOR) will be analyzed as a time-to-event outcome with the duration being measured as the time from measured response to progressive disease, death, or study end.
- 13.3.2.4 Overall survival will be measured from the first day of treatment on the study until death or last known follow up.

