13.5 Sample Size/Accrual Rate

In the dose escalation phase of this study, the sample size is determined by the number of DLTs observed. The minimum sample size for this first part of the study will be 6 patients at DL1 and DL-1 (if necessary), and a maximum sample size of 12 patients. During the dose escalation phase of the combination arm, the minimum number of patients treated will be 3 and maximum will be 6 at each dose level. If the combination is deemed safe and the expansion cohort is enrolled, the sample size will be either 9 or 12 at that dose level. The maximum total sample for the entire study will be 36 patients.

The anticipated complete response (CR) rate in this patient population is approximately 40%. With a minimum sample size of 12 subjects in the combination arm, the probabilities of observing at least 5 responses out of 12 patients (41.7% CR rate) would be 0.42, 0.56, and 0.70 if the true CR rate is 35%, 40%, and 45%, respectively. If the true CR rate is less than 15%, the chance of observing 5 responses out of 12 would be 0.024 or less. This sample size also allows for estimation of the CR rate with precision (half the width of the 95% exact binomial confidence interval) being no wider than 25.5%.

PLANNED ENROLLMENT REPORT

Racial Categories	Ethnic Categories				Total
	Not Hispanic or Latino		Hispanic or Latino		
	Female	Male	Female	Male	
American Indian/ Alaska Native	0	0	0	0	0
Asian	1	0	0	0	1
Native Hawaiian or Other Pacific Islander	0	0	0	0	0
Black or African American	1	2	0	0	3
White	7	13	3	3	26
More Than One Race	0	0	0	0	0
Total	9	15	3	3	30

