13.7 Analysis of Secondary Endpoints

The secondary objectives of this study include describing preliminary antileukemia activity of blinatumomab and nivolumab, and blinatumomab plus both nivolumab and ipilimumab, including the effects on MRD, and assessing preliminary antileukemia activity in an expansion cohort of patients with poor-risk, relapsed or refractory CD19⁺ Pre-B cell ALL. The frequency distribution of responses, including CR, CRi or progressive disease (PD) will be reported by treatment arm and dose level for all patients on study and reported with exact 95% confidence intervals. For patients who have a clinical response, duration of response (DOR) will be analyzed as a time-to-event outcome using the Kaplan Meier method with the duration being measured as the time from measured response to progressive disease, death, or study end. A sensitivity analysis may be performed to evaluate DOR while excluding patients who go on to have an allo-HSCT. Overall survival will be measured using the Kaplan Meier method as the time from the first day of treatment on the study until death or last known follow up.

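### The 12-patient doublet CR rate mixes expansion patients with the six whose 5/6 remissions were reviewed before that expansion was added, and the plan has no caveat or by-cohort display

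*Combined protocol and SAP*

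**What the plan says.** Three parts of the protocol bear on this.

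- **Why the cohort exists.** Section 5.2.2 gives the origin of the doublet cohort: "Based on the review of safety and efficacy data, in discussion with CTEP on 03/13/2019, a separate expansion cohort of an additional 6 patients". It was added alongside the triplet expansion. Section 5.2.1 states: "Based on safety and efficacy data, the dose level A1 was defined as MTD for blinatumomab and nivolumab combination", and gives the data as "1 of 6 patients with DLT; 5 of 6 patients with complete remission". No CR threshold for adding the cohort appears anywhere. Section 5.2.2 also keeps a route that does not involve CR: if the triplet proves intolerable, "then the expansion cohort of an additional 6 patients will be only pursued at the MTD of blinatumomab and nivolumab alone".
- **How many patients.** Section 5.2.1: "An expansion cohort of an additional 6 patients at the MTD of blinatumomab and nivolumab without ipilimumab will be also pursued". Section 13.5 says of an expanded dose level that "the sample size will be either 9 or 12 at that dose level", which counts escalation and expansion patients together. Dose level A1 had six patients, so the total is 6 + 6 = 12.
- **How response is analysed.** Section 13.3.2 reports the response distribution "by treatment arm and dose level for all patients on study will be determined and reported with exact 95% confidence intervals". Section 13.7 repeats this. Neither mentions how the doublet expansion came to be opened. Secondary objective 1.2.2 concerns activity in the expansion cohorts, but section 13 gives no expansion-only estimate to serve it.

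**The concern.** When results in a first group help decide whether a second group is enrolled, the combined rate exists only in the cases where the first group was judged good enough to continue. Given that the cohort opened, the first group's rate tends to sit above the truth, and the combined rate carries half of that excess when the groups are equal in size. An exact binomial interval assumes a fixed sample and makes no allowance for this.

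At stake is how the doublet's activity is read. Preliminary clinical activity is a stated purpose of the expansion. Section 2.2.1.2.2 quotes 44% CR or CRh for blinatumomab alone, and section 13.5 anticipates a CR rate of about 40%. A reader will probably set the 12-patient figure beside those numbers, and nothing in the planned output would say that half of it was known before the cohort was added.

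**Working it through.** **Inputs.** First six patients: 5 CRs (5.2.1). Expansion: 6 patients (5.2.1, 5.2.2). Total at A1: 12 (13.5). Anticipated CR rate: 40% (13.5). Interval: exact (Clopper-Pearson) 95% (13.3.2, 13.7). The opening rule is not documented, so I assume the cohort opens if the first six show at least c CRs and vary c from 2 to 5.

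**The plan's own figures.** For X ~ Bin(12, p), P(X ≥ 5) is 0.417, 0.562 and 0.696 at p = 35%, 40% and 45%, and 0.0239 at 15%. These match the 0.42, 0.56, 0.70 and 0.024 in section 13.5. They assume 12 patients not yet observed. For the doublet, 5 CRs are already in hand, so 5 or more in 12 is certain and these probabilities no longer describe that dose level. (The section speaks of the combination arm and may have meant the triplet.)

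**What 5/6 fixes.** The 12-patient rate must lie between 5/12 = 41.7% (exact 95% CI 15.2% to 72.3%) and 11/12 = 91.7% (61.5% to 99.8%). The lower end already exceeds the anticipated 40%.

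**Bias given opening.** Let X1 and X2 be independent Bin(6, p). The mean of the combined rate given opening is (E[X1 | X1 ≥ c] + 6p)/12, so the bias is (E[X1 | X1 ≥ c] − 6p)/12. At p = 0.40, 6p = 2.4.

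**Coverage given opening.** With n = 12, the lower 95% limit is 34.9% at 8/12 and 42.8% at 9/12, so the interval lies wholly above 40% when the total is 9 or more. The upper limit falls below 40% only for totals of 0 or 1, which cannot occur once c ≥ 2. Coverage is therefore 1 − P(X1 + X2 ≥ 9 | X1 ≥ c). For c = 5: P(X1 = 5) = 0.036864 and P(X1 = 6) = 0.004096, together 0.04096; P(X2 ≥ 4) = 0.1792 and P(X2 ≥ 3) = 0.4557. The miss rate is (0.036864 × 0.1792 + 0.004096 × 0.4557)/0.04096 = 0.2068, so coverage is 79.3%.

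| Assumed threshold c | P(open) | E[X1 given open] | Mean combined rate | Bias (points) | Coverage of 95% CI |
|---|---|---|---|---|---|
| CR not used | 1 | 2.40 | 40.0% | 0 | 96.5% |
| 2 | 0.767 | 2.89 | 44.1% | +4.1 | 98.0% |
| 3 | 0.456 | 3.49 | 49.1% | +9.1 | 96.7% |
| 4 | 0.179 | 4.25 | 55.4% | +15.4 | 92.1% |
| 5 | 0.041 | 5.10 | 62.5% | +22.5 | 79.3% |

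**Expansion patients alone.** X2 does not depend on the first six, so X2/6 has no bias from this source. It is imprecise: 3/6 gives 11.8% to 88.2%, a half-width of 38.2 points.

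**The case against.** The strongest reply is that the documents do not show CR driving the decision. Safety is named with efficacy, one DLT in six already met the 3+3 criterion, and a doublet expansion was foreseen if the triplet failed. If CR played no part, there is no selection bias. CR is a descriptive secondary endpoint with no test, and reporting every treated patient at a dose level is complete and open. All of this stands, and it is why the bias can be given only as a range. It does not remove the point: efficacy is a stated basis, and the DLT rules for A1 in sections 5.2.1 and 13.4 do not require it, so it was an additional input.

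Stronger readings that a reader might infer are not supported:

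- **That the combined rate and its interval are simply invalid.** At a true rate of 40%, coverage stays above 95% for c = 2 or 3 and drops below only for c = 4 or 5.
- **That the size is known from the observed 5/6.** Fixing the first six at exactly 5/6 with a true rate of 40% gives an expected combined rate of (5 + 2.4)/12 = 61.7%, with the interval wholly above the truth 17.9% of the time and coverage of 82.1%. The same numbers would follow in a pre-planned 12-patient cohort that happened to start 5/6. They show that 5/6 is a high draw at 40%; they do not measure selection.
- **That the estimator is biased upward overall.** Averaged over opening and not opening (keeping the six-patient rate if not opened), the bias at 40% is slightly negative, from −0.92 points (c = 5) to −4.15 (c = 3). The upward bias is conditional on opening, which is the situation in which a 12-patient figure is reported.
- **That a regimen will be chosen on this rate.** Section 5.4 ties the recommended dose to DLTs. The 44% figure comes from Ph-negative relapsed or refractory adults, whereas this trial also admits newly diagnosed patients aged 60 or older, Ph-positive disease and MPAL, so that comparison is confounded anyway.

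The plan never uses the word pooled; the combination follows from reading sections 13.3.2, 13.5 and 13.7 together. Nothing forbids a by-cohort table, but none is specified.

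**Conclusion.** The point holds in a limited form and is a cheap improvement. An efficacy-informed decision opened the doublet expansion, and the planned dose-level CR rate includes the patients who informed it, with no caveat. For any CR threshold of 1 or more, the combined rate is biased upward given opening. The range of 0 to +22.5 points assumes a true CR rate of 40%, a simple count threshold of up to 5 in the first six, and independent patients with the same CR rate in both groups. The documents cannot place the trial within that range. The consequence is confined to how a secondary, descriptive activity estimate is read; the primary safety and MTD conclusions rest on DLTs and adverse events.

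**What to change.** In section 13.7, for the doublet at dose level A1:

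1. Report CR with exact 95% intervals separately for the 6 escalation and the 6 expansion patients, beside the 12-patient total.
2. State that the expansion was opened after a review of safety and efficacy data in which 5 of 6 CRs had been seen.
3. Note that the expansion-only rate is free of this selection but imprecise.

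This also supplies the estimate that objective 1.2.2 lacks. I would not make the six-patient rate the preferred estimate: that sets aside half the data, and for a descriptive phase 1 endpoint the trade-off is debatable. The cost is one extra table row, two sentences, and a visibly wide expansion-only interval. No change to design, dosing or enrolment is needed.

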5.2.2 Dose Expansion

An additional 6 patients will be treated at the MTD for both combinations: blinatumomab and nivolumab alone; and blinatumomab/nivolumab plus ipilimumab to gain additional safety information and to explore preliminary biological and clinical activity of these combination therapies. When the MTD of blinatumomab in combination with nivolumab and ipilimumab is determined (either DLB1: Nivolumab 240 mg plus Ipilimumab 1 mg/kg or DLB-1: Nivolumab 80 mg and Ipilimumab 1 mg/kg), an additional 6 patients will be enrolled in an expansion cohort to further characterize safety, tolerability and any preliminary signs of biological or clinical activity of nivolumab and ipilimumab in combination with blinatumomab. However, if the combination of blinatumomab, nivolumab and ipilimumab is found to be intolerable, then the expansion cohort of an additional 6 patients will be only pursued at the MTD of blinatumomab and nivolumab alone (either DLA1: Nivolumab 240 mg or DLA-1: Nivolumab 80 mg) to further characterize safety, tolerability and any preliminary signs of biological or clinical activity for blinatumomab and nivolumab combination.

Based on the review of safety and efficacy data, in discussion with CTEP on 03/13/2019, a separate expansion cohort of an additional 6 patients at the MTD of blinatumomab and nivolumab alone was added to the study in addition to the expansion cohort of nivolumab, ipilimumab and blinatumomab (triple combination) to further characterize safety, tolerability and

any preliminary signs of biological or clinical activity for this combination.

Continuous evaluation of adverse events will be performed throughout enrollment in the expansion cohort. If, at any time, the aggregate rate of treatment-related toxicities meeting DLT criteria exceeds 30% across all subjects treated in the expansion cohort, the safety data will be discussed and further enrollment may be suspended.

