13.4.1 Dose Expansion

Continuous monitoring of safety will be completed during the enrollment and treatment period of each expansion cohort. If it becomes evident that the proportion of patients experiencing a treatment-related toxicity meeting DLT criteria convincingly exceeds 30%, the study will be halted for a safety consultation. The toxicity stopping rule will hold enrollment if the posterior probability of failure being larger than 0.30 is 70% or higher. The prior for this monitoring rule is beta (1,2). This means that our prior guess at the proportion of failures is 33%, and there is 90% probability that this proportion is between 2.5% and 77.6%. The monitoring rule and operating characteristics are given below.

- Stop if 2 out of 2 patients experience a DLT: $\Pr(\text{Risk} > 0.3 \mid \text{Data}) = 0.916$
- Stop if 2 out of 3 patients experience a DLT: $\Pr(\text{Risk} > 0.3 \mid \text{Data}) = 0.837$
- Stop if 2 out of 4 patients experience a DLT: $\Pr(\text{Risk} > 0.3 \mid \text{Data}) = 0.744$
- Stop if 3 out of 5 patients experience a DLT: $\Pr(\text{Risk} > 0.3 \mid \text{Data}) = 0.874$
- Stop if 3 out of 6 patients experience a DLT: $\Pr(\text{Risk} > 0.3 \mid \text{Data}) = 0.806$

Operating Characteristics of stopping rule for toxicity, based on 5000 simulations:

True Toxicity Rate	Probability of declaring treatment too toxic	Average sample size
20%	17%	3.9
25%	26.8%	3.8
30%	34.6%	3.7
35%	43.1%	3.6
40%	52.7%	3.5
45%	61%	3.4
50%	68.8%	3.2

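### Sections 5.2.2 and 13.4.1 set two unreconciled toxicity triggers for the expansion cohorts, and the only printed operating characteristics do not fit a 6-patient cohort

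*Combined protocol and SAP*

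**What the plan says.** Both expansion cohorts have six patients (Section 5.2.2: "An additional 6 patients will be treated at the MTD for both combinations").

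Section 5.2.2 evaluates adverse events continuously. If at any point "the aggregate rate of treatment-related toxicities meeting DLT criteria exceeds 30% across all subjects treated in the expansion cohort", then "the safety data will be discussed and further enrollment may be suspended". It gives no starting number of patients and no operating characteristics. It refers to one expansion cohort, although the section describes two.

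Section 13.4.1 monitors each expansion cohort. If the proportion of patients with DLT-type toxicity "convincingly exceeds 30%, the study will be halted for a safety consultation". The numerical rule is: "The toxicity stopping rule will hold enrollment if the posterior probability of failure being larger than 0.30 is 70% or higher", under a Beta(1,2) prior. The listed boundaries run from "Stop if 2 out of 2 patients experience a DLT", through 2/3, 2/4 and 3/5, to "Stop if 3 out of 6 patients experience a DLT". A table from 5000 simulations gives the stopping probability and average sample size for true rates of 20% to 50%; for example, 17% and 3.9 patients at 20%, and 34.6% and 3.7 patients at 30%.

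Neither section refers to the other.

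**The concern.** Safety and tolerability are the primary objective, and the expansion cohorts exist partly to confirm them. The treatment section and the statistical section each tell the team when accumulating DLT-type events call for action, and the thresholds differ. A team working from 5.2.2 would convene a discussion, and could suspend enrolment, on data for which 13.4.1 asks for nothing. The trial is multi-site, so the section a reader happens to use could decide whether a signal is discussed. The discussion trigger also has no stated probability of firing at an acceptable toxicity rate, so nobody can tell from the protocol how often it would be expected.

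**Working it through.** **Inputs.** Crude threshold 30% (5.2.2); posterior threshold 70% for a rate above 0.30, Beta(1,2) prior and listed boundaries (13.4.1); cohort size 6 (5.2.2).

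**1. Reproduce the printed posteriors.** With x DLTs in n patients the posterior is Beta(1+x, 2+n−x). For integer parameters, Pr(rate > 0.30 | data) = P(Bin(n+2, 0.3) ≤ x). At 2/2 this is 1 − 4(0.027)(0.7) − 0.0081 = 0.916. The other boundaries give 0.837 (2/3), 0.744 (2/4), 0.874 (3/5) and 0.806 (3/6). All five match Section 13.4.1.

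**2. Compare the triggers at every outcome up to n = 6.** All listed boundaries exceed 30% crude, so a hold never occurs without the crude trigger. The crude trigger fires without a listed hold at these outcomes:

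| Outcome | Crude rate | Posterior | Posterior ≥ 0.70? | On the 13.4.1 list? |
|---|---|---|---|---|
| 1/1 | 100% | 0.784 | yes | no |
| 1/2 | 50% | 0.652 | no | no |
| 1/3 | 33% | 0.528 | no | no |
| 2/5 | 40% | 0.647 | no | no |
| 2/6 | 33% | 0.552 | no | no |

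The sections therefore differ at four outcomes. The 1/1 row is a mismatch inside 13.4.1: P(Bin(3, 0.3) ≤ 1) = 0.343 + 0.441 = 0.784 meets its verbal rule, but the list starts at 2/2.

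**3. Probability of triggering in a 6-patient cohort, one patient at a time, true rate p.**

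The crude trigger fires if any of the first three patients has a DLT or, failing that, if at least two of the last three do: 1 − (1−p)³ + (1−p)³ · P(Bin(3, p) ≥ 2). At p = 0.20: 0.488 + 0.512 × 0.104 = 0.541.

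The listed boundaries are crossed if at least two of the first four patients have a DLT, or if exactly one does and both of the last two do: P(Bin(4, p) ≥ 2) + 4p(1−p)³ · p². At p = 0.20: 0.1808 + 0.4096 × 0.04 = 0.197.

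| True rate | Crude (discussion) | Listed boundaries (hold) |
|---|---|---|
| 10% | 29% | 6% |
| 20% | 54% | 20% |
| 30% | 73% | 39% |
| 40% | 86% | 58% |

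**4. Sensitivity to the first look.** Starting the crude check at n = 2 or n = 3 leaves its probabilities unchanged, because one DLT among three is still 33%. If it starts at n = 4, it needs two or more DLTs by n = 6: P(Bin(6, p) ≥ 2) = 34% at p = 0.20 and 58% at p = 0.30. If the 13.4.1 verbal rule is applied from the first patient, so that 1/1 is a hold, the hold probability is 29.6% at p = 0.20 and 47.9% at p = 0.30.

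**5. Check the printed operating characteristics at p = 0.30.** The table states 34.6% and 3.7 patients. For a maximum of 6, the stopping probability is 0.3483 + 0.4116 × 0.09 = 0.385. The average n is the sum of the probabilities of reaching each patient: 1 + 1 + 0.91 + 0.784 + 0.6517 + 0.6517 = 5.0. Truncated at four patients, the values are 0.348 and 1 + 1 + 0.91 + 0.784 = 3.7. The simulation standard error is √(0.346 × 0.654 / 5000) = 0.0067, so 38.5% lies nearly six standard errors from the printed 34.6%, while 34.8% lies well within one. A maximum of 5 gives the same 34.8% but an average of 4.3. The maximum of 4 also fits closely at the other printed rates; at 50% it gives 68.75% and 3.25, against 68.8% and 3.2.

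**The case against.** The strongest defence is that the two rules are nested and differ in force. Section 5.2.2 requires a discussion and only permits suspension. Section 13.4.1 mandates a halt, and only when the excess is convincing. A team can obey both in every case by discussing above 30% and holding at a boundary. Section 12.1 also requires calls at least monthly with investigators and CTEP medical officers to review adverse events. This stands in part: no outcome produces incompatible instructions, and the wording allows a two-tier reading. But the protocol does not state the tiers, and 5.2.2 does not say from what n, or over which patients, its rate is taken.

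Three stronger readings are tempting, and the documents do not support them:

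- A reader might take 54% or 73% as false-hold rates. They are probabilities of prompting a discussion, since suspension under 5.2.2 is optional.
- A reader might infer that 13.4.1 would keep a cohort enrolling at 2/6. The cohort is full at six. At 2/5 one place remains.
- A reader might count five disagreements between the sections. Against the posterior rule there are four; 1/1 differs only from the printed list.

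The size of the gap also depends on assumptions. At a true rate of 20%, 48.8 of the 54.1 points come from a DLT among the first three patients. No stagger is specified within expansion, so several patients may already be on treatment when the first DLT appears. If 5.2.2 means both cohorts pooled, the 6-patient calculation does not describe it.

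**Conclusion.** The point holds as an unreconciled pair of triggers, not as a direct contradiction. On the same data, 5.2.2 can call for discussion and possible suspension while 13.4.1 calls for nothing, at 1/2, 1/3, 2/5 and 2/6. With per-cohort, patient-by-patient monitoring, the discussion trigger is about 23 to 35 percentage points more likely to fire than the listed hold at true rates of 10% to 40% (29.1 − 5.5 = 23.6 at 10%; 73.1 − 38.5 = 34.6 at 30%). With looks only from four patients, the gap narrows to 34.5 − 19.7 = 14.8 points at 20% and 58.0 − 38.5 = 19.5 at 30%.

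Two defects within 13.4.1 do not depend on how 5.2.2 is read. Its list and its verbal rule disagree at 1/1, and its operating-characteristics table matches a maximum of 4 patients when the cohort has 6. As printed, neither trigger has operating characteristics for the planned cohort. The listed posterior probabilities are correct. Which trigger should govern is for the sponsor and investigators.

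**What to change.** Reconcile the two sections in one of two ways:

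- have 5.2.2 refer to the 13.4.1 rule as the only expansion trigger; or
- state that 5.2.2 is a discussion tier separate from the 13.4.1 hold, say whether its rate is per cohort or pooled and from what n it applies, and print its trigger probabilities.

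In either case, make the 13.4.1 list and verbal rule agree at 1/1, by listing that outcome or by stating the n at which monitoring starts. Recompute the operating characteristics for 6 patients per cohort under the rule as finally worded.

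The cost is a few sentences in two sections, one recomputed table and, if two tiers are kept, one added set of probabilities. Sample size and data collection are unaffected.
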